### *20.3 Data security*

Study information will be collected electronically and stored on a secure division drive on the CMH network domain or on Microsoft OneDrive or equivalent; access will be restricted to research team members. All the questionnaires listed above will be collected in REDCap if possible.

Paper data collection forms will be stored in the Endocrine Research Coordinator secure office where only research staff have access. Research records containing PHI will be transported when necessary and will be transported in hospital approved PHI lockboxes per CMH policy. A Certificate of Confidentiality has not been issued for this study.

Data will be stored per the [Record Retention and Management Policy](#) and the Record Retention Schedule.

Approved study staff will have access to research records. Lab & study staff will have access to samples.

The PI is ultimately responsible for receipt or transmission of the data or specimens. Families will mail in the A1C kit which will only contain the Subject ID. When the sample arrives in the lab, research staff is contacted so that the sample can be matched to the MRN so that the sample can be resulted as a “research result” in the electronic health record.

Virtual focus groups will be conducted on a CMH Microsoft Teams channel. Parents/legal guardians and/or participating youth may be in the focus groups. Participants will be instructed to not include any identifying information in their responses. After participants are instructed to change their screenname to a pseudonym, the meeting will be recorded and transcribed directly into the Teams folder, accessible only to the research team. Files will be scrutinized to ensure there is no PHI, censored if necessary, and uploaded directly into Dedoose for coding.

## **21.0 Provisions to Monitor the Data to Ensure the Safety of Subjects**

N/A

The proposed project is a new intervention, therefore we will recruit a Data Safety and Monitoring Board (DSMB) to oversee and monitor the treatment implementation and data collection. We proposed members of the DSMB will include an endocrinologist, a biostatistician, and a certified diabetes educator. Members of the DSMB will be employees of CMH but will not be involved in this study in any way. As part of the DSMB oversight, we propose to meet by every 6 month during the conduct of the study. For each of the meetings, the PIs ([name] and [name]) and biostatistician ([name]) will jointly prepare a summary of the following topics: performance monitoring (a report of subject recruitment/retention, protocol adherence, and quality of data collection procedures), safety monitoring (a review of safety of the participants, including confidentiality and any adverse events or side effects related to the study procedures).

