## 1.0 Study Summary

Study Title	HCT Cash-Only IN centive to promote mealtime insulin DOSE Engagement (HCT COIN2DOSE): a pilot trial
Study Design	Pilot randomized controlled trial
Primary Objective	To determine the impact of HCTCOIN2DOSE and LOAN2DOSE compared to control on the trajectory of glycemic control and treatment engagement among adolescences age 12-17 years who are at risk for a near-term rise in A1C.
Secondary Objective(s)	To determine both the feasibility and usability of HCTCOIN2DOSE and LOAN2DOSE intervention compared to control in adolescents age 12-17 years who are at risk for a significant near-term rise in A1C.
Research Intervention(s)/ Investigational Agent(s)	HCT COIN2DOSE: Utilization of immediate financial incentives to promote mealtime insulin dose delivery, with weekly bonuses for sustained meal dosing behavior LOAN2DOSE: Utilization of loss aversion approach to promote mealtime insulin dose delivery. Participants will start with a virtual bank balance and will have money deducted from the balance when mealtime insulin doses are missed. Additional amounts will be deducted when sustained meal dosing goals are not met.
IND/IDE #	NA
Study Population	Individuals identified by artificial intelligence who are predicted to experience a rise in A1C of greater than or equal to 0.3% in the next 70-110 days using a validated predictive algorithm created via advanced machine learning (random forest) and natural language processing. Individuals must have had the diagnosis of T1D for 6 months and be 12-17.99 years old. Parents of children who meet inclusion criteria may choose to participate in the focus group
Sample Size	A minimum of 36 and a maximum of 72 youth randomized in a 1:1:1 ratio to either the treatment or usual care (control).  Participants and their parents may choose to participate in the focus group. Parents may enroll in the focus group if their child is enrolled in the study. Our aim will be to enroll 5 to 30 parents.
Study Duration for Individual Participants	26 weeks (11-13 weeks intervention and 11-13 weeks observation Participants and/or their parents may choose to participate in a focus group at the end of the study (week 26).

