## **3.0 Background**

### **3.1 Background**

Individuals with T1D can have a tremendous impact on their own health outcomes if they follow their T1D treatment regimen (2) (3) (4). Unfortunately, many adolescents do not adhere to their treatment and experience increased risk for both immediate medical emergencies, long-term T1D-related complications, and mortality (3) (5). Diabetic ketoacidosis (DKA) occurs at a rate of 4.81/100 patient-years in individuals with established T1D and at a rate of 15.83/100 patient years in youth with an A1C  $>9\%$  (6). Adolescents who have poorly controlled T1D are much more likely to develop DKA (3)

(7). While health care professionals can offer guidance and recommendations, it is clear that traditional clinical interactions are not sufficient to promote optimal self-care and adherence for many adolescents (8) with the majority not reaching A1C targets (3). In fact, adolescents with T1D exhibit significant deterioration in glycemic control (aka rising A1C) from age 8 to 18 (9), as shown below.

A number of behavioral interventions have demonstrated utility in improving adherence behaviors in youth with T1D. Improved adherence behaviors are associated with better glycemic control and short and long-term health outcomes (3). On the other hand, lack of adherence can have serious consequences both acutely (DKA or severe hypoglycemic events) and long-term (retinopathy, neuropathy, nephropathy, and cardiovascular disease) (3). Missed mealtime boluses can have devastating metabolic consequences (16).

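### Section 21.0 promises the DSMB a safety review, but the protocol schedules no adverse-event collection, so DKA and severe hypoglycaemia have no stated route to the board, by arm or overall

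*Protocol*

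**What the plan says.** Section 21.0 of the protocol opens with N/A. It then says that, because the intervention is new, a DSMB will be recruited. The principal investigators and the biostatistician jointly prepare a summary for each meeting. Its safety part is described as a review of participant safety, "including confidentiality and any adverse events or side effects related to the study procedures". Nothing says that the summary is broken down by arm.

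The protocol names no source for such events:

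- Table 1 (Section 10.0) lists consent, randomization, CGM, A1C, demographics, questionnaires, device downloads and focus groups. It has no row for adverse events, DKA, severe hypoglycaemia or admissions.
- Section 7.0 describes demographic, A1C, CGM, insulin-delivery, questionnaire and focus-group data, and no event data.
- Section 17.0 lists confidentiality, emotional discomfort, inconvenience and sensor-insertion discomfort as risks. It mentions neither DKA nor severe hypoglycaemia.

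Section 3.1 states that "lack of adherence can have serious consequences both acutely (DKA or severe hypoglycemic events) and long-term". It gives two DKA rates per 100 patient-years: 4.81 for established T1D in general, and a higher one for the poorly controlled, "at a rate of 15.83/100 patient years in youth with an A1C" above 9%. It gives no rate for severe hypoglycaemia.

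**The concern.** The board is promised a safety review, but the protocol schedules no data for the clinical events that its own background section treats as important. The only adverse events named for the board carry a relatedness qualifier. A DKA episode or a severe hypoglycaemic event could be read as background diabetes, and the text does not say whether the board would then see it.

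This matters because the two active arms attach money to insulin boluses (Section 5.0), the trial is unblinded (Section 6.0), and the incentives stop at visit 2. Section 3.2 says the pilot is meant to inform a definitive trial. Without a common event question in all arms, the pilot could not give even a simple table of these events by arm.

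**Working it through.** The protocol states no expected event count, so there is no figure to reproduce. The check asks how many DKA events its own rates imply.

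**Inputs**

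- Sample size (Section 1.0): "A minimum of 36 and a maximum of 72 youth randomized in a 1:1:1 ratio", so 12 to 24 per arm.
- Follow-up (Section 1.0): "26 weeks (11-13 weeks intervention and 11-13 weeks observation", so 26/52 = 0.5 year each.
- DKA rates (Section 3.1): 4.81 per 100 patient-years in established T1D, and 15.83 in youth with A1C above 9%.
- Entry (Section 11.0): A1C above 7.2% and/or a predicted rise of at least 0.3%. The sample may therefore fall between the two rates, and both are shown.

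**Formulas**

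- Expected events = N × 0.5 × rate / 100.
- Probability of at least one event = 1 − exp(−expected), assuming Poisson counts.
- Per arm = total / 3, assuming equal rates in all arms.

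**Results**

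| N | Patient-years | Rate per 100 | Expected, trial | P(≥1), trial | Expected, per arm | P(≥1), one arm |
|---|---|---|---|---|---|---|
| 36 | 18 | 4.81 | 18 × 0.0481 = 0.87 | 58% | 0.29 | 25% |
| 36 | 18 | 15.83 | 18 × 0.1583 = 2.85 | 94% | 0.95 | 61% |
| 72 | 36 | 4.81 | 36 × 0.0481 = 1.73 | 82% | 0.58 | 44% |
| 72 | 36 | 15.83 | 36 × 0.1583 = 5.70 | >99% | 1.90 | 85% |

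So at least one DKA event is more likely than not in every row for the whole trial, although at the lower rate with 36 participants fewer than one is expected. The same calculation cannot be done for severe hypoglycaemia, because the protocol gives no rate.

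**Do the CGM outcomes fill the gap?** Section 4.0 includes percent time below 54 mg/dL as a secondary outcome. It is a share of time, not a count of clinical events. For participants on the blinded device, each insertion gives 10 days. The three insertions in Table 1 give at most 30 days against 26 × 7 = 182 days, or about 16%. Participants with their own CGM may have longer records, but these are still not event records.

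**The case against.** The strongest reply is that the safety sentence is not a closed list. It promises a review of participant safety in general, and the word before the named items introduces examples. The relatedness phrase may qualify only side effects. A reader might infer that Section 21.0 restricts the board to procedure-related events. The text does not support that: it is ambiguous and excludes nothing. A DSMB charter or institutional policy, not at hand, could also supply a route. This stands, and it limits the point to the absence of a stated route.

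Several other inferences are tempting and should not be drawn:

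- **That unblinded investigators decide relatedness.** Section 21.0 says who prepares the summary, not who judges relatedness.
- **That events would be ascertained unequally because active arms upload twice weekly and controls monthly.** Table 1 describes device downloads. Nothing says that an upload prompts an event report.
- **That the protocol's figures predict severe hypoglycaemia.** It is named, but only DKA has a rate.
- **That the meetings are too far apart.** The text says "we propose to meet by every 6 month during the conduct of the study". A board may review accumulated data, and the study is a small pilot classed as minimal risk. Nothing in the documents makes this interval an error.

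Two further points stand. The upper DKA figures require every participant to have an A1C above 9%. With under 1 to about 2 events expected per arm, even complete capture could not establish safety by arm. The rates are also background rates and do not show harm from the incentives.

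The reply does not remove the gap in collection. Clinic visits and the health record may bring some events to light, but no section tells staff to ask about them, record them or pass them on.

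**Conclusion.** The point holds as a gap between what Section 21.0 promises and what the protocol collects. The DKA events implied by Section 3.1, about 0.9 to 2.8 at N = 36 and 1.7 to 5.7 at N = 72, have no stated route to the DSMB, by arm or overall. Nor does severe hypoglycaemia, whose frequency the protocol does not give. The ranges assume a full 26 weeks of follow-up for everyone, Poisson counts, the two Section 3.1 rates as bounds and, per arm, equal rates. The N/A that opens Section 21.0 also conflicts with the DSMB text below it, which is a clerical matter.

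The finding does not show that such events would be withheld from the board, or that the incentives are unsafe. It is a cheap improvement in what is collected and reported.

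**What to change.** 1. Reword the safety item in Section 21.0 so that the board receives all DKA, severe hypoglycaemia and diabetes-related emergency visits or admissions, by arm, regardless of judged relatedness.
2. Add one row to Table 1: the same two or three event questions for all arms, on the REDCap questionnaires already given at visits 2 and 3, with answers checked against the electronic health record. Name this source in Section 7.0.
3. Reconcile the N/A in Section 21.0 with the DSMB text that follows it.

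The cost is some protocol wording, two or three questions at existing visits and a record check. No extra visit or board meeting is needed. The downside is that more background events will be listed, and the by-arm counts will be descriptive only.

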## **22.0 Provisions to Protect the Privacy Interests of Subjects**

Participation in this research study is voluntary. Participants and their parents/legal guardians will be notified of the voluntary status of the research at the onset of the study enrollment and content in process. Any participant or parent who declines to participate will not incur any penalty or loss of benefits to which they are already entitled. No change to the patient's medical care will occur as a result of the participation, or nonparticipation in the study.

Prior to enrollment, participants and their parents/legal guardians will have all risks and benefits clearly explained to them. After explanation for study and consent, subjects and their parents/legal guardians will be offered an opportunity to discuss participation in private, without a study team member present, in order to avoid any potential feelings of bias or coercion. They will be given time to ask questions. They may come back to participate at a later date if they would like to take the study materials home for review prior to agreeing to participate in this study.

For subjects that enroll in the study, they will be informed that they may withdraw at any time without penalty or loss of benefits. Any new information gathered during the course of the study that may impact the subject desire to continue in the study, will be revealed as soon as it becomes available.

All the study information will be kept confidential. Data collected as part of routine diabetes care is protected by CMH's Cerner Electronic Health Record (EHR) and associated policies from the Health Information Management Department (HIM). Data collected specifically for this study will be stored securely as described above.

Participation in this study will be recorded into the EHR in accordance for CMH policy. Any of the research data collected, with the exception of personal health information (PHI), maybe shared in aggregate form in presentations and publications. At the termination of the study, the enrollment, prescreening, and master logs will be destroyed. During the course of the study, the PHI (with the exception of name and MRN) that is collected on individuals who do not wish to participate will be deleted from the prescreening log. The name and MRN will be kept until enrollment is complete so that individuals not interested in participating will not be re-approached for recruitment, and so that MIT can prepare a deidentified, aggregate report of demographic data on individuals who declined participation in the study.

Any PHI in the data collection files will be removed and/or converted to a deidentified number upon completion of the study.

Name, initials, dates of service, date of birth, medical record number, hospital account number, street address, telephone number, and email address may be accessed and/or recorded for research purposes.

HIPAA Authorization for research collection of PHI will be obtained with the permission assent/consent forms.

Focus group participants will be instructed to not include any identifying information in their responses and to use a pseudonym. They will also be instructed not to talk about the discussion outside of the virtual focus group, particularly not to reveal the participation of any other participant that they might know or recognize. They the meeting will be recorded and transcribed directly into the Teams folder, accessible only to the research team. Files will be uploaded directly into Dedoose for coding.

## **23.0 Compensation for Research-Related Injury – NA, Minimal Risk**

N/A

## **24.0 Economic Burden to Subjects**

Subjects will not have any additional costs associated with participation. Participants may complete study visits in the PCRU, via Microsoft Teams, or InTouch Solo (telemedicine platform used at Children's Mercy Hospital that is designed to be used in a clinical setting with a tele-facilitator). There will not be any additional costs to participants associated with study-related procedures.

If the participant damages the Dexcom, they will be asked to return the device to the study team. If a participant loses a device, a note to file will be documented in the participant binder. The participant will be given replacement devices if study budget

allows. They will not be asked to pay for a replacement device or pay for repairs. All participants will be informed that they are expected to return their devices when they have completed the study at the time of informed consent/assent.

## 25.0 Permission/Assent/Consent Process

Permission Assent/Consent will be obtained in the CMH Endocrine Clinic, PCRU, via telephone, or using approved Children's Mercy teleconferencing platforms.

When obtaining consent via telephone, the study team will follow CMH "IRB Permission/Assent/Consent Policy". Permission Assent/Consent will be reviewed thoroughly and participants will be given the opportunity to ask questions. Study staff will emphasize the voluntary nature of participating in research when obtaining consent. CMH Research Policies will be followed.

Assent of children 7 and older will be obtained per CMH policy. Parental/LAR permission will be obtained for all participants

Parents or legal guardians who choose to participate in the focus group discussions will also sign an informed consent.

### ***Consent at 18 years of age, when minor subjects become adults***

Participants who turn 18 while actively participating in study, will sign an Adult Addendum if they choose to continue participation. We are requesting a Waiver of Documentation of Consent for continued use of identifiable data for participants whose active participation has ended.

This protocol, and any subsequent modifications, will be reviewed and approved by the Pediatric IRB at The Children's Mercy Hospital & Clinics. Qualifying patients will be identified by review of daily clinic schedules by research team personnel. Only study personnel will give details about the study to subjects and families. The study will be explained briefly and subjects/parents/legal guardians will be asked whether they are interested in the study. All interested subjects and parents/legal guardians will have the study thoroughly explained using the consent (or permission/assent form as applicable) including risks and benefits. They will then be given copies of the consent to review without staff present so that they have time to discuss with each other. Subjects and parents/legal guardians will also be given the opportunity to ask additional questions after they have read the consent. If subjects and parent agree to participate then consent (or permission/assent form as applicable) will be signed by all required parties and a copy will be given to them. Alternatively, subjects and parents/legal guardians will be given the opportunity to take consents home for further reading, discussion, and decision making at a later date. No pressure will be placed on any subject or family to enroll. All questions will be answered and signatures will be obtained by study staff from the parent before study enrollment.

***Non-English Speaking Subjects - NA***

***Cognitively Impaired Adults - NA***

***Adults Unable to Consent - NA***

## **26.0 Process to Document Permission/Accent/Consent**

In addition to the permission/assent/consent document itself, the consent process will be documented in the medical record and/or research record per CMH policy.

Study personnel will follow CMH “IRB Permission/Accent/Consent Policy” to collect participant written informed consent for their own participation, and parent/caregiver permission for child participation. All of these will be documented on the study informed consent document.

## **27.0 Setting**

The study visits will take place at Children’s Mercy Kansas City diabetes clinics in the Kansas City Metro area, the PCRU, or using approved Children’s Mercy teleconferencing platforms including Microsoft Teams, Polycom, InTouch, Doximity.

## **28.0 Resources Available**

Data resources and tools:

- REDCap (Research Electronic Data Capture) – an internet-based software solution and workflow methodology for designing clinical and translational research databases that is widely used in the academic community
- Library subscriptions to online medical and research websites including Lexicomp, PubMed, Ovid, Google Scholar, and CINAHL will allow for literature review and aid in manuscript development
- Statistics applications such as SAS, SPSS and R will be utilized for data management and analysis
- Approved Children’s Mercy teleconferencing platforms including Microsoft Teams, Polycom, InTouch, Doximity, or other approved platforms

Office: Drs. [name] and [name] will utilize office space allocated to them through their appointment as faculty in the Division of Pediatric Endocrinology & Diabetes. No additional space is requested as part of this grant proposal.

Pediatric Clinical Research Unit (PCRU): The PCRU, constructed in 2012 and opened in January 2013, is located on the ground floor of the Hall Inpatient Tower. Occupying approximately 4,500 ft, it was designed based on the primary goal of creating an ideal environment for all types of clinical research investigation. The unit includes three private patient rooms and one larger three-bed room suited ideally for overnight and multiple sibling studies. The layout of all patient rooms was specifically designed to facilitate patient and family comfort throughout the duration of their stay. The unit includes a large playroom, office space for clinical research faculty and staff members, an exam room, a small laboratory for processing, nutrition room, medication room, soiled utility room, and significant storage space for both patient care supplies and clinical research documents. Facilities are available for phlebotomy, urine collection, initial specimen processing, and temporary specimen storage prior to delivery to the research laboratory. The space is in close proximity to other institutional resources such as the cafeteria, gift shop, and new 3,000 ft Inter-Faith Chapel. Recreational items such as games, crafts, TV, Nintendo, Playstation, and videos are available to entertain children during their stay. In addition, Child Life staff may assist with constructive activities for children. The unit is located one floor below the Pediatric Intensive Care Unit which affords immediate proximity to critical care medicine services should they be required in emergent situations. The unit has been constructed to meet all applicable FDA/ICH guidelines for an early phase study unit and fully meets accreditation standards by The Joint Commission.

General Computer and Network Infrastructure: All faculty and staff have desk top computers running on Windows7 or Windows10 connected to a Children's Mercy client/server LAN with word processing, spreadsheet, database, electronic mail, presentation, and graphical software. Hospital Information Services professional staff support the network, including security and regular backups.

The Windows-based network is configured with security such that a user logging onto the system has a personalized desktop displayed and access to a personal directory on a server that is backed up daily, regardless of which computer in the hospital the user is using. Resources provide full support for electronic data collection, storage, analysis, and exchange. The network is maintained by the Hospital Information Services professional staff.

In addition, CMH has two firewall protected Internet connections that allow transmission of large data and graphics files between CMH investigators and collaborators with I-2 connections. A site on the World Wide Web (<http://www.childrensmerry.org>) is maintained.

Electronic Medical Record (EMR): Children's Mercy uses **Cerner Millennium**, a limited access EMR protected by a closed system with a dual firewall and user sign on authorization. CMH utilizes rigorous security measures, change management procedures, system testing, and a variety of other measures to protect the security and integrity of clinical information in the EMR.

Electronic signatures in the EMR are validated by assignment to unique individuals, and this system employs a secure, computer-generated, time-stamped audit trail. CMH maintains written policies holding study team members accountable and responsible for their actions under their electronic signature and while using the EMR while employed at CMH.

CMH patient care records can be generated and complete copies may be obtained for inspection, review, and copy by a sponsor or their designated representative, as appropriate.

Cerner Millennium complies with the Health Information Portability and Accountability Act (HIPAA) and has been certified to fulfill the HITECH Act of 2009 Meaningful Use requirements.

